There are no adequate data on the developmental risk associated with the use of erenumab in pregnant women or breastfed babies. There are no data on the presence of erenumab in human milk, or on milk production. Pregnant women, breastfeeding women and women planning to become pregnant will be excluded from this study. If a participant gets pregnant, decides to breastfeed her baby or father a child while taking erenumab will be withdrawn from the study and will be monitored and referred to an appropriate practitioner for continued care (see section 9.2 and 9.4.1).

Participants will be closely monitored for any AEs, during the clinic visit and between visits by telephone. Potential risks and discomforts will be clearly stated in the ICF.

TMD examination and pressure pain threshold testing (PPT): A TMD examination will assess muscles of mastication and TMJ sensitivity to manual palpation. The PPT will assess pain applying pressure with the use of an algometer in muscles and the TMJs. Both assessments will be performed on 4 clinic visits. It is expected that these assessments will evoke brief pain or discomfort within a range that is acceptable for the participant. Transient redness or tenderness of the skin may appear after these assessments but none of them is expected to result in lasting discomfort or tissue damage. In addition, the participants may request to stop the examination/test at any time. These assessments will end upon the completion of the modality or upon the participant's request, whichever comes first.

Self-care: It is possible that some participants may feel frustrated if they are unable to incorporate and to understand some self-management approaches.

Questionnaires: It is possible that some participants may experience discomfort associated with answering several questionnaires as well as with being asked personal questions about his/her emotional state and feelings, health history or symptomatology. The participants will be informed that they can choose not to answer any question for any reason.

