4 STUDY DESIGN

60 patients (30 per each arm) aged 18-65 years old of either sex, and any race or ethnicity presenting chronic painful temporomandibular disorders (TMD) will be randomly assigned in a 1:1 parallel, double-blind, phase 2 single center clinical trial, to receive either Erenumab or placebo. Participants will attend 6 clinic visits (Visit 0-Visit 5) over a period of 21 weeks. The study should be completed over a period of 3 years, with an estimated duration of recruitment of 2.5 years.

Participants will be pre-screened in person at the Brotman Facial Pain clinic, the Oral and Maxillofacial Surgery Clinic both at the University of Maryland, School of Dentistry or by telephone. Potentially eligible and interested participants will be scheduled for a Screening and Baseline Visit (Visit 0). During Visit 0, participants will provide informed consent and be evaluated for eligibility; information including demographics, medical history, concomitant medications, and therapies will be collected. In addition, participants will be assessed for pain level, pain symptoms, jaw function, health status, among other measures and a blood sample will be collected. Procedures will include clinical examinations and tests and the dispensation of various questionnaires, all of which are listed in the Schedule of Events (Appendix A).

Participants who show compliance with the Daily Symptom Diary of at least 80% and who meet the pain score (inclusion criteria) for 28 days/4 weeks (baseline period) after Visit 0, will be randomly assigned to one of two groups (Erenumab or placebo) and will be scheduled for Visit 1 within a week of randomization.

At Visit 1, randomized participants will receive the 1st cycle of management and begin a 12-week drug treatment/placebo phase that will be divided into once a month injection/cycle for a total of 3 cycles. During that period, Visits 2-4 will take place, and many of the baseline assessments will be repeated. Between visits, communication will be conducted by telephone. The final study visit, visit 5, will occur 4 weeks after the last assessment (visit 4) and 8 weeks after the last dosage of drug treatment (Visit 3).

The primary endpoint will be the change in a monthly mean pain intensity score derived from the Daily Symptom Diary. Efficacy will be evaluated as the difference between Erenumab arm and the placebo arm in the monthly pain intensity score (on a 0-100 scale) during the 12 week treatment period.

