9. If taking OTC pain medications daily agrees to continue its daily use at the same dosage throughout the study.
 - If a participant is taking an over-the-counter medication daily for management of other type of pain or for prophylaxis of myocardial infarction or stroke, the participant will be encouraged to continue the same usage of that medication throughout the study.
10. Agrees to not start any new prescription medication for the management of pain throughout the study
11. Agrees to not start any injection therapy for the management of TMD (trigger point injections, steroid injections, Botox) during the course of the study
12. Agrees to not use acupuncture for the management of pain during the course of the study
13. Agrees to not have Physical therapy for the management of TMD during the course of the study.
14. Agrees to not start intraoral appliance therapy during the course of the study. If the patient has used a nightguard for more than one month before the study, agrees to continue use it only at night.

15. Females of childbearing potential agree to use one of the following methods of contraception throughout the study: licensed hormonal method, intrauterine device, female or male condoms with contraceptive foam, abstinence, bilateral tubal ligation/occlusion, or vasectomy in partner (if postmenopausal, must not have menstruated for at least 12 consecutive months)
16. Willing and able to understand and comply with all study procedures and be available for the duration of the study

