5.5.2 Handling of Subject Withdrawals or Subject Discontinuation of Study Intervention

Participants withdrawn after randomization will not be replaced. Participants who are withdrawn voluntarily or by the investigator will be discontinued from the study.

Study staff will complete a study disposition form in the eCRF, indicating the reason for discontinuation.

If the patient is a patient from the school and/or is interested in following TMD care at the Brotman Facial Pain clinic, will be referred to the faculty practice clinic front desk for information and to schedule an appointment if wants to.

Unblinding, if required, will be carried out according to the procedures described in

Section 5.4.2. A participant who has an AE at the time of discontinuation will be followed until the event returns to baseline, resolves, or is stabilized. If the AE does not meet one of these outcomes within 30 days after discontinuation or the end of the study, the participant will be referred to an appropriate provider for continued medical care (See section 9.2).

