6.3 Modification of Study Product Administration for a Subject

If a dose of Erenumab is missed, will be administered as soon as possible. Thereafter, Erenumab will be scheduled monthly from the date of the last dose.

The safety profile of erenumab has been favorable in clinical trials and in the post-marketing setting. A limited number of adverse drug reactions (injection site reactions, constipation, muscle spasm, and pruritus) have been identified at low frequencies (< 5%) in clinical trials. In the long-term use of erenumab, the safety profile remained consistent through 5 years of open-label treatment. In post-marketing settings, hypersensitivity reactions (including rash, angioedema and anaphylactoid reactions) and constipation with serious complications have been reported. In addition, oral sores (eg, stomatitis, mouth ulceration, oral mucosal blistering), alopecia and rash (eg, rash papular, exfoliative rash, rash erythematous, urticaria, blister) have been observed in post-marketing surveillance.

Hypertension or worsening of high blood pressure can happen after receiving Erenumab. Hypertension is in our exclusion criteria, however if a new onset of hypertension occurs, the participant will be withdrawn of the study and will be the participant will be referred to an appropriate practitioner for continued care (see section 9.2).

Participants will be closely monitored for any of these AEs, during the clinic visit and between visits by telephone. Potential risks and discomforts will be clearly stated in the ICF. Exclusion criteria includes medical history of constipation or taking medications associated with decrease of G.I motility as well as pre-existent hypertension (See 5.2). If the participant reports a hypersensitivity reaction (rash, angioedema, anaphylaxis), new onset constipation or new onset of hypertension or any of the reactions described above, if there is worsening of TMD signs and symptoms during the 18 weeks of participation or if the participant decides against using Erenumab, he/she will be discontinued from the study (See 2.3.1 and 5.5.2).

The following expected events will not be considered reportable AEs:

- Temporary injection site reactions such as pain, erythema, pruritus after the injection of Erenumab
- Minor bleeding or bruising resulting from the blood draw
- Temporary pain or temporary increases in existing pain prompted during the TMD clinical examination or PPT.

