7.3.2 Visit 2, 2nd treatment/cycle (Day 28/ 4 weeks after Visit 1)

- Review Daily Symptom Diaries in eCRF or collect and review it in paper forms
- Assess compliance with Daily Symptom Diaries
- Review medical history
- Record concomitant medications and therapies
- Take blood pressure and collect weight
- Administer the Symptom Inventory
- Assess and record adverse events (AEs)
- Perform TMD examination
- Perform Pressure Pain examination
- Perform urine pregnancy test (in women of childbearing potential)
- Review 6 questionnaires from Visit 1 in eCRF or collect and review the paper forms
- Provide instruction to complete 6 new outcome measure questionnaires in paper or electronically for review at Visit 3.

- Provide instruction to complete Daily Symptom Diaries electronically or provide them in paper forms
- Deliver the injection of the study drug or placebo
- Schedule next visit

7.3.3 Visit 3, 3rd and final treatment cycle (Day 56/ after 4 weeks from Visit 2)

- Review Daily Symptom Diaries in eCRF or collect and review it in paper forms
- Assess compliance with Daily Symptom Diaries
- Review medical history
- Record concomitant medications and therapies
- Take blood pressure and collect weight
- Administer the Symptom Inventory
- Assess and record adverse events (AEs)
- Perform TMD examination
- Perform Pressure Pain examination
- Perform urine pregnancy test (in women of childbearing potential)
- Review 5 questionnaires from Visit 2 in eCRF or collect and review the paper forms
- Provide instruction to complete 6 new outcome measure questionnaires in paper or electronically for review at Visit 4.
- Provide instruction to complete Daily Symptom Diaries electronically or provide them in paper forms
- Deliver the injection of the study drug or placebo
- Schedule next visit

7.3.4 Visit 4, assessment of last treatment cycle (Day 84/4 weeks after Visit 3)

- Review Daily Symptom Diaries in eCRF or collect and review it in paper forms
- Assess compliance with Daily Symptom Diaries
- Review medical history
- Record concomitant medications and therapies
- Take blood pressure and collect weight
- Administer the Symptom Inventory
- Assess and record adverse events (AEs)
- Perform TMD examination
- Perform Pressure Pain examination
- Collect blood for Cytokine release assay
- Perform urine pregnancy test (in women of childbearing potential)
- Review 5 questionnaires from Visit 3 in eCRF or collect and review the paper forms
- Schedule next visit

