7.5 Withdrawal Visit

An early termination visit will be performed if a participant is suspended before the completion of the study, prior to withdrawal of consent and with the participant's permission. This could happen during a scheduled or unscheduled visit. The investigator, study coordinator or research staff will discuss with the participant to contact the research team in case AE arise after the withdrawal visit. The assessment and procedures of Visit 4 will be conducted at this visit.

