9 ASSESSMENT OF SAFETY

9.1 Specification of Safety Parameters

This study involves the use of Erenumab, a fully human monoclonal antibody that is a CGRP receptor antagonist FDA approved for the prevention of migraine in adults

The participants of this study will be closely monitored and follow up in their clinic visits and between visits with telephone calls. As part of the study outcomes, the study staff will record information regarding AEs. Overall health parameters will be captured on case report forms. These will be completed at every visit and data will be compiled for review by the IRB.

The description of potential risks is described in 2.3 and 6.3. The most common side effects of the use of Erenumab are:

- Injection site reactions: which may include tenderness, pain, redness, itching, bruising, firmness, or hypersensitivity
- Constipation
- Muscle spasms/cramps
- Itching (pruritus)

Allergic reactions can happen within hours to days after using erenumab. Therefore, after the injection is administered, the participant will wait in the room for 20 minutes and the evening of the treatment visit, the participant will receive a follow up phone call and the information will be recorded.

If the participant reports a hypersensitivity reaction (rash, angioedema, anaphylaxis), new onset constipation or new onset of hypertension or any of the reactions described above, if there is worsening of TMD signs and symptoms during the 18 weeks of participation or if the participant decides against using Erenumab, he/she will be discontinued from the study (See 2.3.1 and 5.5.2).

The following expected events will not be considered reportable AEs:

- Temporary injection site reactions such as pain, erythema, pruritus after the injection of Erenumab
- Minor bleeding or bruising resulting from the blood draw
- Temporary pain or temporary increases in existing pain prompted during the TMD clinical examination or PPT.

9.1.1 *Unanticipated Problems*

The Office for Human Research Protections (OHRP) considers unanticipated problems involving risks to subjects or others to include, in general, any incident, experience, or outcome that meets **all** of the following criteria:

- Unexpected in terms of nature, severity, or frequency given (a) the research procedures that are described in the protocol-related documents, such as the IRB-approved research protocol and informed consent document; and (b) the characteristics of the subject population being studied;

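### Contraception is required only while a woman is in the study: 56 days after the last injection for a completer, but close to none for a woman withdrawn soon after a dose

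*Combined protocol and SAP*

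**What the plan says.** Criterion 15 in section 5.1 reads: "Females of childbearing potential agree to use one of the following methods of contraception throughout the study". A list of accepted methods follows. Nothing in the visible text sets a period counted from the last dose.

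The end of the study differs between participants. Section 4 places the final visit "8 weeks after the last dosage of drug treatment (Visit 3"). For those who leave early, section 5.5.2 says: "Participants who are withdrawn voluntarily or by the investigator will be discontinued from the study". Section 5.5.1 allows withdrawal at any time.

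Some exits are required by the protocol. Sections 6.3 and 9.1 list the triggers, beginning "If the participant reports a hypersensitivity reaction (rash, angioedema, anaphylaxis), new onset constipation or new onset of hypertension", and add worsening TMD and a decision against the drug. On timing, section 9.1 says: "Allergic reactions can happen within hours to days after using erenumab".

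On the reason for contraception, section 2.3.1 says: "There are no adequate data on the developmental risk associated with the use of erenumab in pregnant women or breastfed babies". At the withdrawal visit, section 7.5 has staff "discuss with the participant to contact the research team in case AE arise after the withdrawal visit". It says nothing about contraception.

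**The concern.** Exposure is set by the date of the last injection, but the requirement is tied to the date of leaving the study. Two women with the same last injection can therefore have very different required protection, and the one who leaves soonest after exposure has the least. That includes women the protocol itself removes because of a reaction shortly after a dose.

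This is a matter of participant safety and does not affect the efficacy analysis. The risk is conception shortly after exposure to a drug for which the protocol says adequate developmental data do not exist. Staff working from the protocol would apply criterion 15 as written.

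**Working it through.** **Inputs**
- Injections at Visits 1, 2 and 3, on Days 0, 28 and 56 (sections 7.3.1 to 7.3.3; the last is headed "Visit 3, 3rd and final treatment cycle (Day 56/ after 4 weeks from Visit 2").
- Visit 4 on Day 84 (section 7.3.4) and Visit 5 on Day 112 (section 7.4).
- The requirement ends when the participant leaves the study (criterion 15 read with section 5.5.2).

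**The plan's own interval.** Visit 5 minus Visit 3 = 112 − 56 = 56 days = 8 weeks. This matches section 4. Two of the Appendix A table headers use Days 60 and 120 instead, which gives 120 − 60 = 60 days and the same conclusion.

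**Early exit.** Required cover = exit day − day of last injection. Shortfall against a completer = 56 − cover.

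| Exit | Last injection | Required cover (days) | Shortfall (days) |
|---|---|---|---|
| Day 1 | Day 0 | 1 − 0 = 1 | 55 |
| Day 3 | Day 0 | 3 − 0 = 3 | 53 |
| Day 27 | Day 0 | 27 − 0 = 27 | 29 |
| Day 57 | Day 56 | 57 − 56 = 1 | 55 |
| Day 84 (Visit 4) | Day 56 | 84 − 56 = 28 | 28 |
| Day 112 (completer) | Day 56 | 112 − 56 = 56 | 0 |

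With dosing on schedule, cover is 0 to 28 days for an exit between Visits 1 and 3, and 0 to 56 days for an exit between Visits 3 and 5.

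**Whether another provision closes the gap**
- The early-termination pregnancy test (Appendix A) detects an existing pregnancy at one moment. The visit needs the participant's permission (section 7.5). If she withdraws consent and declines it, no further evaluation is done (section 5.5.1).
- Recording of events for 30 days after participation (section 9.2) captures a pregnancy but does not prevent one.
- Section 9.4.5 promises follow-up to outcome for a pregnancy that begins while the participant is receiving study drug. Conception after withdrawal may fall outside that wording.
- Exclusion criterion 20 keeps out women planning pregnancy, but it governs entry only.

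**The case against.** The strongest reply has four parts.

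1. The near-zero figure depends on a reading. Criterion 15 is an undertaking given at entry, it does not define when the study ends, and nothing says outright that the undertaking lapses at withdrawal. This is fair, but section 5.5.2 points to that reading, and a safety rule open to it needs clarifying.

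2. Eight weeks has no pharmacological basis in the documents. They give no half-life or washout, and 56 days is simply where the follow-up visit falls. This stands: the shortfall measures unequal treatment of women with the same exposure, and it does not show that 56 days is necessary or sufficient.

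3. The instruction may sit in the consent form, which cannot be seen, or in the redacted parts of section 9.4. This also stands as a possibility. It does not change what criterion 15 says.

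4. The practical risk may be small. Half the participants receive placebo, several permitted methods (intrauterine device, tubal ligation, partner vasectomy) continue regardless of trial status, and the timing of hours to days is stated for allergic reactions, not for constipation or hypertension. Pregnancy counts as an SAE in section 9.4.5, so the section 7.5 advice on adverse events might prompt a report. Women who leave with an adverse event are followed up under section 5.5.2. These points limit the likely number affected. However, assignment is blinded, so the rule has to suit women on active drug, and reporting and follow-up come after conception.

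**Conclusion.** The concern holds. As written, required contraceptive cover after the last injection runs from near 0 to 56 days depending on when a woman leaves, and a woman who leaves 1 to 3 days after a dose has 53 to 55 days less than a completer.

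This rests on on-schedule dosing and on the requirement ending at withdrawal. The number of women affected cannot be derived from the documents, and they do not show whether 56 days is long enough. The change is worth making because the gap concerns safety, early exit is foreseeable, and closing it costs little.

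**What to change.** Reword the duration in criterion 15 to: throughout the study and for at least 8 weeks after the last injection of study product, including after early withdrawal. Eight weeks gives early leavers what completers already have. The sponsor's clinicians should lengthen it if they judge that necessary.

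Repeat the instruction in the early-termination procedures (section 7.5) and, if it is not already there, in the consent form.

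The cost is protocol wording, with consent wording if needed. The downside for participants is a contraception commitment of up to 8 weeks after early withdrawal. After withdrawal of consent the trial cannot enforce it, so it should be agreed at entry. No visits or procedures are added.

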5.2 Subject Exclusion Criteria

1. Participants with a history of congestive heart failure, rheumatoid arthritis or uncontrolled diabetes.
2. Participants with serious hepatic, respiratory, hematologic or immunologic illnesses, an unstable cardiovascular disease, or any other severe acute or chronic medical or psychiatric condition or laboratory abnormality that may increase the risk associated with trial participation or Erenumab or may interfere with the interpretation of trial results and, in the judgment of the investigator, would make the participant inappropriate for entry into this trial
3. Participants with high blood pressure, history of abnormal electrocardiograms, history of heart conductance defects, malignant disease, chronic constipation, IBSc or any other severe acute or chronic medical or psychiatric condition or laboratory finding that may increase the risk associated with trial participation with Erenumab
4. Participants with active malignancy of any type or a history a malignancy (with exception of participants with malignancy surgically removed with no evidence of recurrence within 5 years before enrollment).
5. History of facial trauma or orofacial or orthognathic surgery within the previous 6 months
6. Patients with dental pain
7. Patients with trigeminal neuralgia or other neuropathic pain in the craniofacial area
8. Patients with rheumatoid arthritis or any systemic arthritis
9. Patients with chronic migraine with and w/o aura following the ICHD-3 criteria treated or not treated with medication
 - Without excluding headache attributed to TMD

10. Participants currently taking or have previously taken Erenumab or other CGRP monoclonal antibody (mAmb) or currently taking a CGRP-Receptor antagonist (gepants) for migraine prevention. CGRP-Receptor antagonist (gepants) for acute use for migraine are allowed.
11. Patients with hypersensitivity to Erenumab
12. Patients who have received the Botox injection protocol in the masseters and/or Migraine protocol within 3 months prior screening and baseline visit.
13. Used injections for management of TMD (trigger point injections, steroid injections) within 2 weeks prior to the Screening and Baseline Visit
14. Has commenced a new daily prescription medication for the management of pain within 30 days prior to the Screening and Baseline Visit
15. Has commenced intraoral appliance therapy for the management of facial pain within 30 days prior to the Screening and Baseline Visit
16. Patient currently undergoing active orthodontic treatment (passive retainers are permitted)
17. Treatment for drug or alcohol abuse within the last year
18. Has been treated with another investigational drug or treatment within 30 days prior to the Screening and Baseline Visit
19. Patients sensitive to Latex
20. Patient is pregnant, planning to become pregnant or breastfeeding
21. Anything that, in the opinion of the investigator, would place the participant at increased risk or impede the participant's full compliance with or completion of the study.

